8. SAFETY CONSIDERATIONS

8.1 ADVERSE EVENTS

Adverse events will be monitored through the administration of a weekly questionnaire and reporting of events throughout the study period. If participants report any adverse events, these must be reported to the University of Sydney HREC. These must be reported even if they may be unrelated to the intervention.

Serious adverse events resulting in hospitalisation or death must be reported to the University of Sydney HREC within 24 hours, even if they may be unrelated to the intervention. In both cases, participants will be followed-up by phone or in-person until resolution of the adverse event.

8.2 Risks of the study

Gastrointestinal Discomfort and Adverse Reactions to Foods:

This research study involves a slight variation of the participant's dietary intake. In the unlikely event that a severe adverse reaction to the intervention food item occurs, participants will be requested to cease the intervention for follow up with the study Dietitian and PhD candidate ([name]) in consultation with the study Physician. Participants with a history of food allergy or sensitivity to the intervention food item (olive oil) and any food items or supplement derived from olives will be identified during screening and will not be eligible for the study. Participants with a special dietary requirement resulting in their inability to adhere to the intervention will also be excluded.

The use of a fat based food item for isocaloric replacement to their normal diet in this study was determined in part due to the lower likelihood of resulting in gastrointestinal discomfort to the participant compared to other food items e.g., dairy, red meat, insoluble fibre. The study model proposed was chosen as it had the potential to cause the least amount of burden to participants as opposed to a comprehensive dietary change, in addition to being a novel model of identifying the impact of specific dietary constituents. Participants will receive one on one counselling with the study Dietitian throughout their enrolment in the study, and individualized support will be provided. Dietary assessment and intervention is a vital part of this study as it is the topic investigated, and as such will need to be included.

Muscle Soreness and Injury:

As with any exercise testing there are potential risk of injury. Prior to any physical testing participants will undergo a physician screen. Additional medical information will also be sought from the participants nominated GP or specialist overseeing their health to ensure that there are no contra-indications to exercise testing. A physician supervised stress test will also be performed as part of the screening procedure.

The exercise testing and stress test may result in some muscle soreness and fatigue. There is also a small risk of musculoskeletal soreness or injury during the physical function test,

however this is rare during the type of testing proposed for this project. To minimize risk of injury, participants will be supervised by a trained and experienced health professional during all testing procedures. Any activities which are contra indicated to the participant will also not be performed, with a note justifying the decision recorded in the assessment sheet. Any events of episodes during testing will be followed up by the study physician. Exercise testing is required to identify any potential changes to functional capacity and strength during the study, including any changes occurring as a result of improved gastrointestinal symptoms and inflammation.

Activity monitoring:

There is a small chance that wearing the activity monitor on the lower back under the bandage might cause some slight skin irritation from the tape residue and location. We will ensure that the tape is applied neatly and without tensing the skin to minimise any discomfort due to the tape application.

Blood sampling:

An experienced professional will collect the blood samples from the participant's vein. Rarely will blood leak from a vein, but this is easily rectified by applying pressure over the vein. All procedures will be performed under sterile conditions with highly experienced and qualified professionals. Blood sampling will be performed while the participant is lying down to avoid light-headedness or fainting during the procedure, and participants will be requested to move their legs after periods of lying down. Sharps and biological waste will be disposed of in their corresponding bins which are located throughout the testing site in C block.

Blood collection is necessary to this study to determine physiological response to the intervention and provide further insights to any associated biochemistry in relation to the gut microbiota which would not be achieved just by tracking the dietary changes alone. In the unlikely event that participant distress occurs from this process, information to counselling can be provided. Blood test results from the study may be forwarded to the participants nominated healthcare professional for further investigation if deemed appropriate upon receiving informed consent from the participant (e.g., assessments for vitamin D, in which deficiency often occurs in this cohort).

Radiation:

This research study involves exposure to very low amounts of radiation from the DXA x-rays. The effective dose of radiation from this study is very low at about 0.02 millisieverts (mSv) done once at baseline. For comparisons, about 2 mSv (100x higher) is experienced each year by the public from natural sources as part of everyday living. No harmful consequences have been demonstrated at this level and the risk is minimal. Participants will be requested to inform the researchers if they have participated in any other research study in the past 5 years where they have been exposed to radiation. Participants will also be advised to show the Participant Information Statement from this study to research staff of any other study they may wish to volunteer for in the next 5 years. DXA is included as part of this research due to the insights it provides on a participant's bone density and risk of fracture, in addition to allowing the team to assess body composition in response to the intervention. Osteoporosis is a known extra-

intestinal manifestation of IBD, and as such accurate assessments of bone mineral density is valuable as standard of care with considerations to fracture risks and quality of life. Due to complications in food absorption in relation to the chronic condition we are investigating, individuals with IBD are at a higher risk of developing osteopenia and osteoporosis. Identifying this risk benefits both the research team and the participant's current care, and results will be communicated with the participants nominated healthcare professional for follow up if consent has been provided by the participant. Radiation safety approval received on 15/01/2019, RSC number RSC1901.

Adverse Effects:

During each test procedure, and at regular intervals throughout the program, we will ask participants to inform us of any side effects that they may experience. Participants will be advised that they must contact the study staff immediately if there are any unusual health experiences, injury or bad effects. This notification should take place whether or not they believe that the problem is related to the program or from some other cause. Prior to any testing, the study physician will review participant's medical history to make sure they are medically ready for the study procedures.

In the event of an injury or other misadventure, we will contact the participant's GP and /or gastroenterologist, and may recommend an appropriate course of action in consultation with the GP as necessary. In the event of any adverse event participants will be able to contact the study physician [name] [name] on [name].

9. OUTCOMES AND SIGNIFICANCE

9.1 OUTOMES

Table 2 illustrates the COLONIC study primary and secondary outcomes. Table 2 illustrates the outcomes that will be assessed and the time points at which each outcome will be assessed (Baseline, 4 weeks, 8 weeks).

Primary Outcomes	Time Point
Disease Activity for Ulcerative Colitis Partial Mayo Score for Ulcerative Colitis	Baseline, 4 weeks, 8 weeks
Microbiome Dysbiosis Evaluation of gut bacterial profiles. Participants will be required to produce a stool sample into a plastic bag, ensuring no fluid or urine comes in contact with the sample. Participants will be provided with a collection kit with instructions. The fecal sample will be stored at the University of Sydney freezers at -80°C if produced onsite, or stored in participant's freezers then transported to the University of Sydney during the clinic date. It will then be transported to Medlab Clinical ([name]) in batches where they will be stored at -80°C and then analyzed	Baseline, 4 weeks, 8 weeks

once there are enough samples to make the run financially viable (approximately every 10 samples).
	

Secondary Outcomes
	

Nutrition 3-day weighted food records, 1 Month Retrospective Food Frequency Questionnaire (FFQ), Probiotic foods and nutraceutical inventory, Risk of Malnutrition via the Mini Nutritional Assessment (MNA) Diet quality as determined by the CSIRO Diet Index Polyphenol content of the diet as determined by FoodWorks Oleic acid intake as determined by FoodWorks Diet Inflammatory Index (DII) Plasma Oleic Acid levels Faecal SCFA content Plasma Hydroxytyrosol sulfate and Tyrosol as determined by ultra-HPLC-ESI-MS/MS Self-reported symptoms diary for food intolerances and adverse reactions Food Choice Questionnaire Food Related Quality of Life Questionnaire for IBD (FR-QoL-29)
	
Baseline, 4 weeks, 8 weeks

Anthropometry Waist, upper-arm and calf circumferences, height, weight, Resting Heart Rate
	Baseline

Body composition Whole body and regional lean and adipose tissue, Bone density in the lumbar spine and hip. Dual-energy X-ray absorptiometry (DXA)
	Baseline

Inflammatory profile Cytokines/adipokines including tumour necrosis factor and interleukins 1, 6, 10 and 12. C-Reactive Protein Erythrocyte Sedimentation Rate Faecal calprotectin TNF α Faecal IgA and IgA coating bacteria analysis Faecal Cytokines LPS in blood Serum levels of Folate Serum levels of Calcium Serum levels of vitamin D Blood cell count
	Baseline, 4 weeks, 8 weeks

Neuropsychological outcomes Inflammatory Bowel Disease (IBD) Questionnaire, Depressive Symptoms via will be assessed via patient health questionnaire (PHQ-9) and Hospital and Anxiety Depression Index (HADS), Quality of life via the SF-36® Health Survey, Fatigue via the IBD Fatigue Scale. Sleeping patterns via the PSQI
	Baseline, 4 weeks, 8 weeks

Physical activity participation Objective physical activity 7-day physical activity monitoring using Axivity MEMS 3-axis accelerometer and physical activity logs
	Baseline, 4 weeks, 8 weeks

Maximal aerobic capacity (VO₂peak) Graded treadmill test to voluntary fatigue with indirect calorimetry
	Baseline

Muscle strength 1-repetition maximum tests for the chest press, seated row, shoulder press, lat pull-down, leg press, leg extension, and leg flexion.
	Baseline

Adverse events All adverse events related and not related to the intervention. Gathered using weekly health status check and reporting of events throughout the study period.
	Weekly throughout the study

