We calculated effect size based on a 2 point (22%) reduction in the Partial Mayo Score (less than half of the mean difference cited in literature), with alpha 0.05 and beta 0.8. Effect size was calculated to be 1.25, with a sample size of 12 participants per group (24 individuals with Ulcerative Colitis randomized to either the intervention or usual care) required to determine changes in disease activity post intervention. Accounting for a 16% dropout rate which occurred in both studies selected, we will aim to recruit 28 participants with Ulcerative Colitis.

With consideration to those without a history of Inflammatory Bowel Disease, we will also aim to recruit an equal number of participants. Due to the limited evidence available on the effects of EVOO consumption on the gut microbiome and inflammatory markers in apparently healthy individuals, the recruitment number of apparently healthy controls are not based on any hypotheses on the differences between those living with UC and non-IBD cohorts subjected to EVOO consumption or dietary intervention. In total, we will aim to recruit 56 participants for this study; 28 individuals with UC and 28 individuals without a history of IBD.

Expected duration of the study and start times

It is expected that the study will take four years to complete. This includes 6 months to set up the study, including recruitment and training of the study personnel, procuring study resources, and preparation of the recruitment and study materials.

It is expected that recruitment will begin no later than April 2019. We are aiming for a conservative estimate of 1 participant per week, and means all participants will be recruited by June 2020, however additional time has been allocated to account for delays related to other investigations, work and travel arrangements, and recent changes to therapy.

The baseline assessments will start in April 2019 and end latest by August 2020.

The post-intervention assessments will start in May 2019 and end by November 2020, with additional time allocated to account for unexpected delays in recruitment and assessment.

The main outcome publication will be prepared by early to mid-2021. Table 2 illustrates the overall project schedule.

Table 2. Colonic Project Schedule

	2018	2019				2020				2021
	Oct-Dec	Jan-Mar	Apr-Jun	Jul-Sep	Oct-Dec	Jan-Mar	Apr-Jun	Jul-Sep	Oct-Dec	Jan-Mar
Study protocol and ethics approval	X	X								
Set-up of the study	X	X								

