2 Weeks	Baseline Clinic Visit 2 (must be at least 8 days after Clinic 1)	
In person physical and health screen (duration ~5-6 hours)
 
 - Fasted assessments - Anthropometry - Collection and review of assessment 1 forms 
Location: The University of Sydney, Faculty of Health Sciences, Lidcombe

	
Randomisation into 1 of 4 Groups (UC Usual Care, UC Intervention, Control Usual Care, Control Intervention)
	
4 Weeks	Intervention (Week 1-4)	
Intervention: Replacement of usual free fats with the study fats
 
Usual Care: Maintain all usual daily activities
 
Weekly teleconference for all study groups (duration 15-20 minutes) Review new symptoms, changes to current therapy, lifestyle, visits to a healthcare professional

2 Weeks	Mid-Point Assessment (Week 5, over 2 days)	
Repeat a portion of assessments in Clinic Visit 1 and Clinic Visit 2
 
 - Fasted assessments - Nutrition assessment & food diaries - Stool collection - Questionnaires 
Location: The University of Sydney, Faculty of Health Sciences, Lidcombe

4 Weeks	Washout Period (Week 6-9)	
Intervention 1 and 2: Collection of all unused study fats, resume usual daily behaviour prior to study
 
Usual Care: Maintain all usual daily activities
 
Weekly teleconference for all study groups (duration 15-20 minutes) Review new symptoms, changes to current therapy, lifestyle, visits to a healthcare professional

2 Weeks	Final Assessment Clinic Visit 1	
In person physical and health screen (duration ~3-4 hours)
 
 - Physician review (as required) - Questionnaires (food intake, IBD symptoms, affect) - 3-day Weighted Food Diary Instruction - Stool Collection Instructions - 7-day Axivity Monitor Attachment 
Location: The University of Sydney, Faculty of Health Sciences, Lidcombe

	Final Assessment Clinic Visit 2 (must be at least 8 days after Clinic 1)	
In person physical and health screen (duration ~2-3 hours)
 
 - Fasted assessments - Anthropometry - Collection and review of assessment 1 forms 
Location: The University of Sydney, Faculty of Health Sciences, Lidcombe

End of Study Participation		

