11. FUNDING/SUPPORT BEING SOUGHT OR SECURED

Funding will be sought for analysis of blood and stool (gut microbiome). Until funding is secured to perform the analyses, these samples will be stored in -80 degree freezers.

Grants that will be targeted include:

- Kenneth Rainin Foundation
This encourages collaboration among health researchers from across disciplines to advance the study of inflammatory bowel disease. Awards are worth up to USD 300,000 each.
<http://krfoundation.org/health/grants/synergy-award/>
- Crohn's and Colitis Foundation of America
These provide established researchers with funds to generate sufficient preliminary data to become competitive for funds from external sources. Awards are worth up to USD 115,830 per year for one to three years.
<http://www.cafa.org/science-and-professionals/research/grants-fellowships/senior-research-awards.html>
- Innovations in inflammatory bowel disease research
Crohn's and Colitis Foundation of Canada | Fondation Canadienne des Maladies Inflammatoires de l'Intestin
These support innovative projects that have the potential to improve the diagnosis, therapy and prevention of inflammatory bowel disease. Grants are worth up to CAD 50,000 for a maximum period of one year.
http://www.cffc.ca/site/c.ajlRK4NLLhJ0E/b.6326399/k.4BD2/Opportunities_For_Researchers.htm

- International Organisation for the Study of Inflammatory Bowel Disease
These support members of the organisation in conducting research relevant to inflammatory bowel disease. Grants are worth up to USD 200,000 for a maximum period of one year. Preference will be given to small grants of up to USD 50,000. Salaries to cover principle or co-investigator salaries will not be covered.
<http://www.ioibd.org/grants/>

- Crohn's and Colitis Foundation of America
These support innovative proposals that lead to improvements in the prevention, diagnosis or therapy of Crohn's Disease or Ulcerative Colitis.
<http://www.cafa.org/science-and-professionals/broad/funding/>

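### The run rule for stool samples (about every 10) does not keep a participant's three samples together, so run-to-run variation adds avoidable noise to microbiome change, and the rule is not reconciled with storage until funding.

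*Protocol*

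**What the plan says.** Protocol section 9.1 lists microbiome dysbiosis as one of two primary outcomes. It gives "the time points at which each outcome will be assessed (Baseline, 4 weeks, 8 weeks" as the schedule, so each participant supplies three stool samples. Samples go to the laboratory "in batches where they will be stored at -80°C and then analyzed" "once there are enough samples to make the run financially viable (approximately every 10 samples". That is a trigger based on cost. The section does not say which samples make up a run, whether a participant's samples stay together, or how arms are spread over runs.

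Section 11 says money for the blood and stool analyses is still to be sought, and adds: "Until funding is secured to perform the analyses, these samples will be stored in -80 degree freezers". Neither section refers to the other.

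Three further statements set the timing:
- Section 6.4: "In total, we will aim to recruit 56 participants for this study; 28 individuals with UC and 28 individuals without a history of IBD".
- Section 6.4: "We are aiming for a conservative estimate of 1 participant per week, and means all participants will be recruited by June 2020".
- Section 7.1, Figure 2: "Mid-Point Assessment (Week 5, over 2 days". A washout over weeks 6 to 9 follows, and then two final clinic visits.

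Section 6.5 analyses continuous outcomes with a repeated-measures mixed model for the Group x Time interaction.

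**The concern.** The quantity of interest is each participant's change in the microbiome. If the samples being compared are measured in one laboratory run, any shift specific to that run cancels in the difference. If they are measured in different runs, both runs' shifts stay in the difference and add to its variance. A rule that starts a run whenever about 10 samples are in hand, with samples from one person several weeks apart, looks likely to split nearly every participant's set.

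Precision is at stake for a primary outcome with only 28 participants per disease group, 14 per arm. The mediation analysis in section 6.5 uses the same microbiome changes, so measurement noise there would weaken the estimated indirect effect. Run assembly has to be settled before the first run, because it cannot be undone later.

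**Working it through.** **1. The plan's own timetable.** 56 participants at 1 per week from 1 April 2019 means the last one enters 55 weeks later, on 20 April 2020. This agrees with completion by June 2020. Spreading recruitment over the whole window (1 April 2019 to 30 June 2020, 65.1 weeks) gives 56 / 65.1 = 0.86 per week. The planned rate is therefore taken as 0.86 to 1 per week.

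**2. Number and pace of runs.**
- Samples: 56 x 3 = 168, so 168 / 10 = 16.8, or about 17 runs. Sections 2 and 6.2 give 60 participants; that would be 180 samples and 18 runs.
- Steady-state arrival at 1 per week: 3 samples per week, so a run fills in 10 / 3 = 3.3 weeks. At 0.86 per week: 10 / (3 x 0.86) = 3.9 weeks.
- Gap between a participant's successive samples: 4 weeks by section 9.1, or about 5 to 6 weeks by Figure 2.

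The gap is longer than the time a run takes to fill, so successive samples usually fall in different runs.

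**3. Share of participants whose samples are split.** All samples were placed on a calendar and cut into consecutive runs of 10 by arrival. Recruitment was evenly spaced or random (Poisson), with no dropout. Filling by arrival is an assumption, because section 9.1 gives only the trigger.

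| Recruitment per week | Sample spacing | Baseline and mid-point in different runs |
|---|---|---|
| 0.86 to 1 | Figure 2 (week 5, weeks 10 to 11) | 94 to 96% |
| 0.86 to 1 | 4 and 8 weeks | 91 to 95% |
| 0.5 (assumed) | either | 47 to 80% |
| 0.25 (assumed) | either | 18 to 49% |

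A separate simulation with stratified blocks gave 93 to 95% with 5-week spacing and 88 to 92% with 4-week spacing. At the planned rate, roughly 88 to 95% is a fair summary. The exceptions are mainly the first and last few participants.

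**4. Visit mix within runs.** With 56 participants at 1 per week and samples at weeks 0, 5 and 10.5, the first run is about 75% baseline samples. The second is about 45% baseline, 45% mid-point and 10% final. Runs 3 to 15 hold 30 to 40% of each visit. The last two contain about 10% and 0% baseline samples. So 13 of 17 runs are balanced over visit.

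**5. Effect on the variance of change.** Let *s* be the share of within-person, between-sample variance due to run. For samples in different runs, the variance of change relative to same-run processing is 1 / (1 - *s*) if run effects are independent across participants:
- *s* = 0.10: 1.11
- *s* = 0.20: 1.25
- *s* = 0.30: 1.43

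Runs are shared by both arms, so part of the run effect cancels in the arm contrast. Simulation of the between-arm change among UC participants left about 88 to 94% of the run variance in place. With that fraction *f*, the ratio is 1 + *f* x *s* / (1 - *s*):
- *s* = 0.10: 1 + 0.88 x 0.111 = 1.10, to 1 + 0.94 x 0.111 = 1.10
- *s* = 0.20: 1 + 0.88 x 0.25 = 1.22, to 1 + 0.94 x 0.25 = 1.24
- *s* = 0.30: 1 + 0.88 x 0.429 = 1.38, to 1 + 0.94 x 0.429 = 1.40

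The increase is therefore roughly 10 to 40%. The range of *s* is assumed; the protocol gives no run variance.

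**The case against.** - **Rolling analysis may never happen.** Section 11 holds samples until funding is secured. If funding comes late, many samples will be on hand together. This stands, and it makes the figures above conditional. It does not remove the problem: section 9.1 still would not say how stored samples are assigned to runs.
- **Randomisation protects the arm comparison.** A reader might infer that run effects bias the intervention effect. The protocol does not support that. Section 6.2 allocates 1:1 in blocks of four or six within disease and sex, so both arms pass through the same runs. The result is noise in Group x Time, not bias.
- **Run is not generally confounded with visit.** A reader might infer that early runs are baseline and late runs follow-up. That is true only of the first one or two and the last two of about 17 runs; the rest are balanced. Bias in the UC-versus-healthy comparison would need unequal recruitment over time, and section 6.3 plans to recruit the two groups alongside each other.
- **Not every participant is affected.** A few early and late participants would share a run at the planned rate, and many more would if recruitment were slow.
- **A run term can be left to the statistical analysis plan.** Fair, and its absence from the protocol is no finding. It could recover part of the loss, but with about 17 small runs it uses degrees of freedom in a small trial.
- **Home freezers.** Section 9.1 allows samples to be frozen on site at -80°C "or stored in participant's freezers then transported to the University of Sydney during the clinic date". One might infer that storage varies within a person or by arm, but nothing in the protocol suggests that use of the two routes differs by arm, so the point does not rest on it.

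**Conclusion.** The point holds as a matter of precision. Followed as written, with runs filled by arrival at 0.86 to 1 participant per week, the rule puts baseline and mid-point samples in different runs for roughly 88 to 95% of participants. This adds avoidable technical noise to within-person change in a primary outcome. The loss cannot be fixed from the protocol; for an assumed run share of 10 to 30%, the variance of change rises by roughly 10 to 40%. In sample-size terms that is like losing 1 - 1/1.10 = 9% to 1 - 1/1.40 = 29% of participants for this outcome. The conclusion rests on arrival-order filling, on the planned rate of recruitment, and on funding being in place early enough for rolling analysis. Sections 9.1 and 11 leave that last condition open and need to be reconciled in any case.

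**What to change.** In section 9.1, replace the rule of analysing about every 10 samples with these steps:

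1. Store samples at -80°C until a participant's three samples are complete, or until all samples in the trial are in.
2. Analyse each participant's set in a single run. Three sets make 9 samples, close to the run size already planned, and 56 / 3 gives about 19 runs instead of 17.
3. Spread sets from the four arm-by-disease cells across runs in random order.
4. Record the run for every sample.

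Reword sections 9.1 and 11 so that they describe one handling route, including what happens if funding comes late.

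The cost is later microbiome results, longer storage and about two more runs if the 9-sample layout is used. Section 11 already foresees storage at -80°C.
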